Therapeutic use of amniotic fluid and the amniotic membrane has existed in medicine for decades in many different capacities (Shimberg 1938). Some applications include healing of the eye, soft-tissue wounds, and bone fractures (Karaçal et al. 2005; Kerimoğlu 2008). Recently, amniotic epithelial cells have been shown to express stem cell markers of pluripotency, including octamer-binding protein 4 (*Oct-4*) and *Nanog* (Miki and Strom 2006; Miki 2011). Cells isolated from the amnion are able to differentiate into all three germ layers: endoderm, mesoderm and ectoderm (Toda et al. 2007).

Amniotic fluid and membrane contain mesenchymal stem cells (MSCs), which may be useful in graft material for bone fusion for several reasons. They have been shown to have osteoinductive and osteogenic properties, and therefore can regenerate bone. They have been shown to selectively adhere to bone substrate and are unlikely to be rejected since they are immune privileged (they do not express human leukocyte antigen (HLA) class II molecules). Also, stem cells from amniotic origin have low risk of tumorigenicity (Siegel et al. 2007). Finally,

stem cells from an amniotic source do not pose ethical issues, as there is no risk to the mother or fetus.

NuCel® is a commercially available (NuTech Medical, Birmingham, AL) source of MSCs derived from human amniotic fluid in combination with morselized amniotic membrane tissue. In addition to stem cells, this tissue contains collagen, proteoglycans, hyaluronic acid, trophic proteins including bone morphogenetic proteins (BMPs), and growth factors.

Therefore, the goal of the proposed research is to use NuCel® in the bone graft material applied to patients undergoing posterolateral lumbar spine fusion, to assess its ability to promote bone fusion. Its safety and efficacy will be compared to a standard allograft material routinely used for this surgery.

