### ***B. Hypothesis***

We hypothesize that the NuCel® group will report, on average, Oswestry Disability Index (ODI) scores 10% lower than those of the DBM group. Assuming a baseline ODI score of 52 (SD=8) for the DBM group, 90% power and an a Type 1 error rate of 5%, a sample size of 42 patients (21 per group) would be sufficient to detect a 10% difference between groups using a repeated measures design with 6 measurement points. To account for drop-out, loss to follow-up, and/or refusal to complete study documents at follow-up, we plan to recruit a total of 60 patients (30 per treatment arm).

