## Radiological outcomes

Radiographs of the lumbar spine will be assessed at the time of surgery (intra-operatively) and at 1 and 2 months (anterior-posterior and lateral) and at 3 months (flexion-extension) after surgery to detect any spinal instrumentation failure. CT scans of the lumbar spine will be taken at 6 and 12 months post surgery to assess fusion. Assessment will be performed by an independent radiologist who will be blinded to the treatment and clinical condition of the participants. The radiologist will score fusion according to the following categories: no fusion, any fusion, or solid fusion.

The table below shows the time line for each data collection activity:

|                                              | Pre-op | Intra-op | Post-op months (range in days) |                      |                      |                            |                             |
|----------------------------------------------|--------|----------|--------------------------------|----------------------|----------------------|----------------------------|-----------------------------|
|                                              |        |          | 1
(25-
35
days)       | 2
(55-65
days) | 3
(85-95
days) | 6
(170-
190
days) | 12
(355-
375
days) |
| Oswestry Disability Index (ODI)  | X      |          | X                              | X                    | X                    | X                          | X                           |
| Pain rating scales               | X      |          | X                              | X                    | X                    | X                          | X                           |
| Neurological exam                | X      |          | X                              | X                    | X                    | X                          | X                           |
| CT scan                          |        |          |                                |                      |                      | X                          | X                           |
| X-ray                            |        | X        | X                              | X                    | X                    |                            |                             |

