#### ***E. Statistical Analysis***

We will first compare the demographic and pre-operative clinical characteristics of the NuCel® and DBM groups to evaluate randomization fidelity. If any characteristics are found to be statistically significant between the groups, this will be accounted for in the analyses of the primary and secondary outcomes. We will describe all categorical variables as percentages and continuous variables with means and standard deviations.

To evaluate our primary outcome we will use a linear mixed model with ODI score as the dependent variable and treatment group and time as independent variables. Mixed models are often preferred over a two-way ANOVA because they allow for incomplete data from participants and do not require a strictly normal distribution in the dependent variable. This model will also be used to evaluate the effect of treatment group on pain scores over time. Statistical significance will be set at  $p < .05$ .

We will report the frequency of observed fusion at the 6-month and 12-month follow-up periods via CT scan by treatment group. If our sample size allows, we will compare the NuCel® and DBM groups on fusion rates at each time point using Fisher’s Exact tests. Statistical significance will be set at  $p < .05$ .

We will report the frequency of adverse events experienced by the NuCel® and DBM groups including negative changes in neurological exam (sensory and motor) findings during the follow-up period.

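### The 90% power claim rests on an unstated correlation and effect by visit, and the visit-averaged ODI analysis loses power if the benefit is delayed

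*Combined protocol and SAP*

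**What the plan says.** Section B hypothesises that "the NuCel® group will report, on average, Oswestry Disability Index (ODI) scores 10% lower than those of the DBM group". The sizing starts from this: "Assuming a baseline ODI score of 52 (SD=8) for the DBM group". With 90% power and 5% type 1 error it arrives at 21 per group, described as "sufficient to detect a 10% difference between groups using a repeated measures design with 6 measurement points". Recruitment is raised to 30 per group to cover losses.

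Section C takes the ODI pre-operatively and at months 1, 2, 3, 6 and 12, which makes up the six points.

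Under Radiological outcomes, "CT scans of the lumbar spine will be taken at 6 and 12 months post surgery to assess fusion". The films at months 1-3 look for instrumentation failure. The Introduction says NuCel is being used "to assess its ability to promote bone fusion".

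The primary analysis in section E is a "linear mixed model with ODI score as the dependent variable and treatment group and time as independent variables". No treatment-by-time term, baseline covariate or primary time point is named.

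**The concern.** A model with group and time main effects gives a single treatment coefficient, which is in effect an average over every visit included. Its power depends on two things the plan does not state: how strongly a patient's ODI scores correlate between visits, and how large the treatment difference is at each visit.

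Two features of the schedule make this matter. First, the pre-operative score counts as one of the six points, yet randomisation makes the expected difference there zero. Second, three of the five post-operative visits come before the plan first assesses fusion, the process the graft is meant to promote. If benefit takes time to appear, those visits pull the average towards zero. A true difference of the planned size at the later visits could then go undetected and be read as no benefit.

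**Working it through.** **Inputs from the documents.** Section B: mean 52, so 10% is 0.10 × 52 = 5.2 points; SD 8, variance 64; 21 per arm; 5% error. Section C: six ODI points, five of them post-operative.

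**Assumptions added here.** Two-sided test; equal correlation ρ between any two visits; SD 8 at every visit; no missing data among the 21 per arm.

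**Formulas.** The variance of a k-visit mean is V = 64 × (1 + (k−1)ρ)/k. With pre-operative ODI as covariate it is V = 64 × [(1 + (k−1)ρ)/k − ρ²]. Power is from the noncentral t with 2n − 2 degrees of freedom and noncentrality d/√(2V/n), where d is the difference averaged over the visits used.

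**Step 1: the plan's own figure.** A single measurement needs 2 × (1.960 + 1.282)² × 64/5.2² ≈ 50 per arm (normal approximation), so the reduction to 21 comes from repeated measures. With k = 6 and d = 5.2 at all six points, 21 per arm gives 90% at ρ ≈ 0.28: V = 64 × (1 + 5 × 0.28)/6 = 25.6, power 90%. At ρ = 0.30 it is 89%; at ρ = 0.5 it is 77%. The claim can therefore be reproduced, but only with a correlation the plan does not give.

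**Step 2: the pre-operative point.** With a full 5.2 points at all five post-operative visits and zero before surgery, the six-visit average is d = 5.2 × 5/6 = 4.33. Power is 78% at ρ = 0.27 and 76% at ρ = 0.30.

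**Step 3: five post-operative visits only.** At ρ = 0.27, V = 64 × (1 + 4 × 0.27)/5 = 26.6; at ρ = 0.30, V = 28.2. Baseline-adjusted, V is 22.0 and 22.4. At 21 per arm and ρ = 0.27-0.30:

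| Assumed pattern | Average d | Unadjusted | Baseline-adjusted |
|---|---|---|---|
| 5.2 at all five visits | 5.2 | 87-89% | about 94% |
| Half at months 1-3, full at 6 and 12 | 5.2 × (3 × 0.5 + 2)/5 = 3.64 | 58-61% | 68-69% |
| Months 6 and 12 only | 5.2 × 2/5 = 2.08 | 24-25% | 28-29% |

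**Step 4: the alternative contrast.** For the baseline-adjusted mean of months 6 and 12 with d = 5.2, V = 64 × [(1 + ρ)/2 − ρ²], which is 36.0 at ρ = 0.27 and 32.0 at ρ = 0.5. Power at 21 per arm is 78% and 83%. The adjusted five-visit average with a constant effect stays at about 94% over the same range of ρ.

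**Step 5: the other reading of the hypothesis.** If 5.2 points is already the average over the five post-operative visits, averaging costs nothing. A late-only effect would then have to be 5.2 × 5/2 = 13 points at months 6 and 12.

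**The case against.** The strongest reply is that section B hypothesises a difference on average. Taken literally, 5.2 points is the visit-averaged difference and the time course is irrelevant to power. That reading is open, and it stands. Its consequence is the 13-point late effect of step 5, a quarter of the assumed mean of 52, which the plan does not discuss.

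Second, CT timing shows when fusion is first measured, not when it begins or when disability could diverge. Nothing says that ODI benefit comes only through fusion, and the Introduction also describes growth factors and trophic proteins in the product. This stands too, so the delayed patterns are assumptions.

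Third, section E does not exclude an interaction; it says the same model will assess the effect of group on pain over time. If an interaction were fitted to all six points, an omnibus test would have about 58% power at 21 per arm for the late-only pattern (ρ about 0.3). The text names only the two main effects, however, and this test is not what section B was sized for.

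A reader might infer that the design assumed a full effect at every visit, or that a fusion-driven benefit would most likely be missed. The documents support neither: they give no formula and no effect by visit, and the result depends on the pattern and on baseline adjustment. Nor do they show that months 6 and 12 must be the primary contrast. That choice costs power (78-83% against 94% at 21 per arm) if the effect is constant.

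**Conclusion.** The point holds as one of incomplete specification with a material sensitivity. The 90% figure cannot be checked without a correlation, and it is reproduced only at about 0.28 with the full difference at all six points, including one where none is expected. Allowing for that point alone brings the six-visit average to about 76-78% at 21 per arm. This follows from the schedule and randomisation and needs no assumption of delay, though it does take 5.2 points as the difference at each post-operative visit.

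Sensitivity to delay is real, but its size is conditional: from little or no loss for a constant effect over the five post-operative visits to 24-29% power for a late-only effect. The half-early pattern lies between, at 58-69%. All these figures rest on SD 8, a two-sided 5% test, equal correlation of 0.27-0.30 and 21 evaluable per arm. The extra nine per arm are there to cover losses and should not be counted as added power.

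**What to change.** In section E, model the five post-operative ODI scores with treatment, visit and treatment-by-visit, and use pre-operative ODI as a covariate instead of an outcome point. Report the treatment difference at each visit, including months 6 and 12. Do the same for the pain scores.

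Name the primary contrast in advance. The baseline-adjusted average over the five post-operative visits keeps the existing hypothesis. The baseline-adjusted mean of months 6 and 12 is an option if the sponsor expects a delayed effect.

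In section B, replace the six-point statement with the power of the chosen contrast, and state the correlation, sidedness and effect assumed at each visit. At correlation 0.27-0.5 and 21 evaluable per arm, that is about 94% for the five-visit adjusted average under a constant effect, or 78-83% for the adjusted mean of months 6 and 12.

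The cost is slightly more analysis work and possibly a less favourable stated power. No visits, patients or data are added.

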### ***C. Study Variables***

#### Clinical outcomes

The following data will be collected at the time of enrollment (pre-operatively), and at 1, 2, 3, 6 and 12 months after surgery: 0-10 numeric pain rating scale for low back and leg pain, Oswestry Disability Index (ODI), and a neurological exam (sensory and motor evaluation). We will also record any adverse events (infection, inflammation, radiculopathy, etc.) that occur intra-operatively through 12 months. Demographic information including gender, age, diagnosis, spinal level for surgery, will be recorded directly into an Excel spreadsheet for each patient.

## Radiological outcomes

Radiographs of the lumbar spine will be assessed at the time of surgery (intra-operatively) and at 1 and 2 months (anterior-posterior and lateral) and at 3 months (flexion-extension) after surgery to detect any spinal instrumentation failure. CT scans of the lumbar spine will be taken at 6 and 12 months post surgery to assess fusion. Assessment will be performed by an independent radiologist who will be blinded to the treatment and clinical condition of the participants. The radiologist will score fusion according to the following categories: no fusion, any fusion, or solid fusion.

The table below shows the time line for each data collection activity:

|                                              | Pre-op | Intra-op | Post-op months (range in days) |                      |                      |                            |                             |
|----------------------------------------------|--------|----------|--------------------------------|----------------------|----------------------|----------------------------|-----------------------------|
|                                              |        |          | 1
(25-
35
days)       | 2
(55-65
days) | 3
(85-95
days) | 6
(170-
190
days) | 12
(355-
375
days) |
| Oswestry Disability Index (ODI)  | X      |          | X                              | X                    | X                    | X                          | X                           |
| Pain rating scales               | X      |          | X                              | X                    | X                    | X                          | X                           |
| Neurological exam                | X      |          | X                              | X                    | X                    | X                          | X                           |
| CT scan                          |        |          |                                |                      |                      | X                          | X                           |
| X-ray                            |        | X        | X                              | X                    | X                    |                            |                             |
| Adverse events                   |        | X        | X                              | X                    | X                    | X                          | X                           |

Required for research purposes

Standard of care procedure

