## I. INTRODUCTION

Lumbar degenerative disc disease is a common disorder that may cause debilitating symptoms. Although there is discrepancy in the prevalence estimates of the morphological changes associated with degeneration (Battie et al. 2004), lumbar degenerative disc disease is a major cause of chronic disability (Modic and Ross 2007). Risk factors include genetic predisposition, trauma, impaired nutrition of the intervertebral disk, mechanical loading and aging (Battie et al. 2004; Modic and Ross 2007). Patients with lumbar disc disease most commonly present with low back pain and radiculopathy, but many are asymptomatic (Modic and Ross 2007).

When conservative measures such as medication and physical therapy fail, lumbar spinal surgery is used to treat degenerative disc disease. Spinal fusion surgery limits movement of the vertebrae adjacent to the affected intervertebral disc. It typically consists of spinal instrumentation to secure the vertebrae, and bone graft material, to allow the vertebrae to fuse together (Rutherford et al. 2007).

One of the major controversies surrounding lumbar spine fusion is the choice of ideal graft material used to facilitate fusion. Commonly studied properties of graft materials include osteoconduction (scaffolding for bone re-growth), osteoinduction (growth factors that induce bone growth), and osteogenesis (living cells that produce new bone); (Vaccaro 2002). An ideal allograft material is one that is safe, effective in forming bone, forms bone where intended without excessive bone growth, can integrate with the host, and is cost effective.

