There are several commercially available bone graft substitutes with differing properties. Allograft is bone obtained from cadaveric sources, which has been treated to decrease its immunogenicity and risk of disease transmission. It is osteoconductive, minimally osteoinductive, slower to incorporate and produces more variable results than autogenous bone graft (Vaccaro 2002; Miyazaki and Tsumura 2009). Ceramics have been used in spinal fusions, as they are osteoconductive, available in large quantities and are sterile. However, they are brittle and can withstand little force (Vaccaro 2002; Miyazaki and Tsumura 2009). Demineralized bone matrix (DBM) is both osteoconductive and osteoinductive. It is produced from cortical allograft bone that has undergone acid extraction, removing its mineral component, but retains many proteins, including growth factors (Miyazaki and Tsumura 2009). Osteoinductive growth factors have also been used as bone graft substitutes, and the most studied and used factor is recombinant human bone morphogenetic protein-2 (rhBMP-2). Since its introduction commercially in 2002, rhBMP-2 has shown rapid and robust bone fusion, and gained widespread use, despite its high cost. However, reports of serious complications have emerged, including ectopic bone formation, infection, urogenital events, carcinogenicity and others (Carragee et al. 2011). This lead to the Yale University Open Data access (YODA) Project to re-analyze all the clinical data gathered by the manufacturer of rhBMP-2 (Infuse; Medtronic). The results were published in June 2013, in a special edition of the Annals of Internal Medicine. Two independent groups (Fu et al. 2013; Simmonds et al. 2013) found that rhBMP-2 was not better than autogenous bone graft in terms of fusion, pain or function, but posed an increased risk of adverse events. Other emerging options for bone graft substitutes include autologous platelet concentrate, mesenchymal stem cells and gene therapy (Miyazaki and Tsumura 2009).

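### The research CTs are to be read only for fusion, so a trial that promises a safety comparison plans no systematic, blinded look for misplaced or excessive bone

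*Combined protocol and SAP*

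**What the plan says.** Section I (Introduction) sets the background in four steps.

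- An ideal graft, among other properties, "forms bone where intended without excessive bone growth, can integrate with the host, and is cost effective".
- Of rhBMP-2 it says: "reports of serious complications have emerged, including ectopic bone formation, infection, urogenital events, carcinogenicity and others".
- Of NuCel it says that "this tissue contains collagen, proteoglycans, hyaluronic acid, trophic proteins including bone morphogenetic proteins (BMPs), and growth factors".
- It closes by stating that the safety and efficacy of NuCel will be compared with those of a standard allograft.

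Section II.C (Radiological outcomes) schedules CT at 6 and 12 months, with assessment of fusion as the stated purpose. The reader is an independent radiologist blinded to treatment and clinical condition, and the score is this: "The radiologist will score fusion according to the following categories: no fusion, any fusion, or solid fusion". The plain films up to 3 months look for instrumentation failure.

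Section II.C (Clinical outcomes) records adverse events of any kind from surgery to 12 months, with an open list of examples that includes radiculopathy. The time-line table schedules this at the same 6- and 12-month visits as the CTs.

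Section II.E reports CT results as fusion frequency by group. On safety it says: "We will report the frequency of adverse events experienced by the NuCel® and DBM groups including negative changes in neurological exam".

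**The concern.** The Introduction gives a reason to ask whether a graft makes bone in the wrong place, and the trial takes the scans on which a reader could look for it. The blinded reader is not asked the question. The fusion grade cannot record it either: bone that bridges the segment and also enters the canal or foramen would be graded on the bridging alone.

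What is at stake is the safety conclusion. A report of no excess adverse events could be read as evidence that NuCel does not produce misplaced bone, although nobody had looked for it systematically. The primary ODI comparison is not at stake.

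**Working it through.** The plan gives no figure for this outcome. Its only calculation, 42 patients enlarged to 60 (Section II.B), concerns ODI and has no bearing here. The check is mainly a comparison of text, followed by arithmetic on what an added item could show.

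**Step 1. Each planned route by which misplaced or excessive bone could be recorded.**

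| Route | Stated purpose or content | Systematic for misplaced bone? | Done by someone stated to be blinded? |
|---|---|---|---|
| CT at 6 and 12 months (II.C) | Three-grade fusion score | No | Yes |
| Plain films up to 3 months (II.C) | Instrumentation failure | No | The blinded-reader sentence follows the CT sentence and may cover these too |
| Adverse-event record (II.C, II.E) | Open-ended, through 12 months | No; needs symptoms or a chance finding | Not stated |
| Neurological exam (II.C, Sources of Bias) | Sensory and motor deficits | No; shows a consequence, not the cause | Not stated; Sources of Bias concedes possible evaluator bias |

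No route asks anyone to look for bone outside the fusion bed. The documents also describe no path from the radiologist's reading to the adverse-event record. A symptomatic case could be entered simply as radiculopathy, with nothing tying it to bone formation.

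**Step 2. Scans already available.** Section II.B plans 60 patients, 30 per arm, and II.C plans two CTs each: 60 × 2 = 120 at most. The time-line table marks them as done for research.

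**Step 3. What a zero count would mean.** With no cases in n patients, the one-sided 95% upper bound is 1 − 0.05^(1/n).

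- n = 30 (all recruited in one arm): 1 − 0.05^(1/30) = 0.095, or 9.5%.
- n = 21 (the per-group number the ODI calculation requires): 1 − 0.05^(1/21) = 0.133, or 13.3%.

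The upper limit of a two-sided 95% exact interval uses 0.025 in place of 0.05: 11.6% for n = 30 and 16.1% for n = 21.

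**Step 4. Chance of seeing at least one case in an arm of 30.** The documents give no event rate, so the rates are assumed and shown as a range. The formula is 1 − (1 − p)^30.

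| Assumed true rate p | Chance of at least one case |
|---|---|
| 1% | 26% |
| 5% | 79% |
| 10% | 96% |
| 20% | 99.9% |

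**Step 5. Chance of a formal difference.** With 30 per arm, two-sided Fisher's exact test gives p = 0.052 for 5 versus 0 and p = 0.024 for 6 versus 0. Only a large imbalance would reach 0.05, so the item belongs with descriptive safety reporting.

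**The case against.** The strongest reply is that the plan is not silent on harm. Adverse events are collected without restriction through 12 months, at the same visits as the CTs, and reported by arm together with neurological worsening. Symptomatic ectopic bone therefore has a route, as would a chance finding on CT that someone reported. This stands. A reader might infer that the harm would go wholly uncounted, and the documents do not support that. What is missing is systematic, blinded ascertainment, which matters most for cases without symptoms.

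A reader might also infer that the protocol itself names ectopic bone as a risk of NuCel. It does not. Ectopic bone is listed for rhBMP-2, excessive growth appears only in the description of an ideal graft, and BMPs are one item in a list of NuCel constituents with no concentration given. The connection is an inference. It is a reasonable one in a trial that promises a safety comparison.

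Two further readings go too far. Misplaced bone is not the only safety matter that imaging can show, since the plain films are taken to find instrumentation failure. Nor would surplus bone count only to an arm's credit: bone pressing on a nerve could worsen ODI, leg pain and the neurological exam, and ODI is the primary outcome. The one-sidedness is confined to the fusion grade, which is compared between groups only if numbers allow.

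Finally, the added count would be imprecise and would alter no planned test. That is true, and it limits what the item can claim. A zero from scans read for the finding still carries a stated bound; a zero from scans not read for it carries none.

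**Conclusion.** The point holds as an omission in safety ascertainment. The plan has no systematic, blinded CT assessment of misplaced or excessive bone in either arm, although up to 120 CTs will be taken and read by a blinded radiologist. Open-ended adverse-event reporting is the only planned route to recording it, and asymptomatic cases would be missed.

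This rests on two assumptions. The first is that the reading will contain no more than Section II.C describes, since the form itself is not in the documents. The second is that the stated BMP content makes the question relevant to NuCel.

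The size is modest. No sample size, planned test or primary conclusion changes. What changes is whether the trial may say anything about misplaced bone. As planned it can speak only to cases that came to notice; with the item, a zero count in 30 would exclude rates above about 9.5% (one-sided 95%).

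**What to change.** In Section II.C (Radiological outcomes), add to the same blinded CT reading at 6 and 12 months, in both arms, one item scored present or absent, with location, for bone outside the intended posterolateral fusion bed (for example canal or foramen).

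In Section II.E, report at each time point the number of patients per arm with the finding, over the number with a CT read, with exact confidence intervals. Label it a descriptive safety outcome and keep it separate from the fusion grade.

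The cost is a slightly longer read and some incidental findings to deal with. No extra patients, scans or readers are needed. The report should state the low precision openly, so that a zero or a small difference is not taken as evidence of equal safety.
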